7.2. Research Objectives

The following matters will be investigated in patients receiving BESPONSA under actual conditions of use after marketing:

(1) Occurrence of adverse events (AEs) (including the following evaluations):

Background characteristics possibly affecting the onset of liver disorder including VOD/SOS, myelosuppression, infections and hemorrhage, and grade ≥ 3 events based on the CTCAE v4.0 as well as risk factors for early death of HSCT patients after BESPONSA treatment

(2) Efficacy (hematologic remission rate and survival)

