8.7. Observation Period

Observation period: The observation period will be 52 weeks for patients not undergoing HSCT within 52 weeks after the start of BESPONSA treatment or until 52 weeks following HSCT for patients undergoing it within 52 weeks after the start of BESPONSA treatment. For a patient starting BESPONSA treatment before 30 April 2020 who is transferred to another hospital during the observation period, the conclusion of the agreement on the implementation of this investigation should be requested to the hospital to which the patient has been transferred, and data from there should be collected to the extent possible.

(1) Treatment phase

From treatment initiation to Day 28 post-treatment: Safety (e.g., AEs) and efficacy (hematologic remission and survival)

(2) Follow-up phase

From Day 29 post-treatment to Week 52 (patients who did not undergo HSCT before Week 52) or 52 weeks after HSCT (patients who underwent HSCT before Week 52): Safety (VOD/SOS) and efficacy (survival)

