## 2.1. Study Design

- **Target population**

*All patients who received this drug will be included in this survey.*

- **Survey period**

*The scheduled periods of this survey are as follows:*

*Survey period: From the date of launch of this drug to 5 years\**

*Registration period: From the date of launch of this drug to the time of lifting of approval conditions for all-case survey\**

*\*: Patients who started to receive this drug on or after May 1, 2020 will only be registered.*

The protocol may be changed to terminate the registration only period, but this change will not affect the SAP.

- **Observation period**

*Observation period: The observation period is to be 52 weeks for patients who did not undergo hematopoietic stem cell transplant (HSCT) within 52 weeks after the start of the treatment with this drug and up to 52 weeks after HSCT for patients who underwent HSCT within 52 weeks after the start of this drug. If patients who started to receive this drug on or before April 30, 2020 are transferred to another hospital during the observation period, the transferred hospitals will be requested to conclude a contract for the conduct of this survey, and the information at the transferred hospitals will be collected as much as possible.*

*[1] Treatment Period*

*From the start of treatment to Day 28 post-final dose: For assessments of safety (e.g., adverse events) and effectiveness (hematologic response, survival time)*

*[2] Follow-up period*

*For 52 weeks from 29 days after the final dose (for patients who did not undergo HSCT by 52 weeks after the start of treatment) or for 52 weeks after HSCT (for patients who underwent HSCT by 52 weeks after the start of treatment): For assessments of safety (VOD/SOS) and effectiveness (survival time)*

The starting point for the 52 week follow-up after HSCT is the day of the last HSCT performed within 52 weeks after the start of this drug.

- **Safety specification**

See Protocol Section 7.1.

- **Sample size and its rationale**

*Of the patients who have received this drug, a total of 176 patients with relapsed or refractory CD22 positive (CD22+) acute lymphocytic leukemia (ALL) will be included in the safety analysis set. In consideration of dropouts during the survey, 200 patients will be registered.*

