- Peripheral blast count before conditioning for the first HSCT after the start of this drug [≤ 1000 /µL, > 1000 /µL, not performed]
- Myeloblast count before conditioning for the first HSCT after the start of this drug [≤ 50%, > 50%, not performed]
- Time from the date of final dose of this drug to the date of the first HSCT after the start of this drug [< 4 weeks, ≥ 4 weeks to < 8 weeks, ≥ 8 weeks to < 12 weeks, ≥ 12 weeks to < 16 weeks, ≥ 16 weeks]
- Treatment cycles [1 cycle, 2 cycles, 3 cycles, 4 cycles, 5 cycles, 6 cycles, > 6 cycles]
- Treatment cycles [≤ 3 cycles, ≥ 4 cycles]
- Dosing of > 1.8 mg/m^2 per cycle [absent, present] (Considered to be present, if there is a cycle of > 1.8 mg/m^2 per cycle during the treatment period.)
- Pregnancy [absent, present] \* Pregnancy during the treatment period. Limited to cases in which information on pregnancy is collected
- Best overall response [complete remission (CR) or complete remission with incomplete hematologic recovery (CRI), progression or relapse, indeterminate/other, not performed]
- Minimal residual disease (MRD) [negativity achieved, negativity not achieved, test not performed]
  - \* Irrespective of the result of best overall response.
- Best overall response and MRD [CR/CRI achieved and negativity achieved, CR/CRI achieved and negativity not achieved, progression/relapse and negativity achieved, progression/relapse and negativity not achieved] \* "Indeterminate/other" and "not performed" are excluded.
- Adverse drug reactions that occurred during the treatment period - liver disorder as a safety specification [absent, present]

Subgroup analyses of hematologic response and MRD will be performed for the following patient characteristics and other factors:

- Age [< 15 years, ≥ 15 to < 65 years, ≥ 65 years]
- Age [< 18 years, ≥ 18 to < 55 years, ≥ 55 years]
- Age [< 15 years, ≥ 15 to < 40 years, ≥ 40 years]
- Disease name [Relapsed CD22+ acute lymphocytic leukemia (ALL), refractory CD22+ ALL]
- Chromosome karyotype [normal, t (4;11), unknown]
- Chromosome karyotype [Philadelphia chromosome positive, negative, unknown]\* Philadelphia chromosome is considered positive if the chromosome karyotype is t(9;22).
- Hemoglobin level immediately before the start of this drug [< 10 g/dL, ≥ 10 g/dL, not performed]
- Platelet count immediately before the start of this drug [< 10 × 10^4/µL, ≥ 10 × 10^4/µL, not performed]

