### **8.2.3. Safety analyses**

Adverse drug reactions (ADRs) and adverse events (AEs) that occurred in the following periods will be collected for summary: for ADRs and AEs other than VOD/SOS, those that occurred from the start of this drug to 28 days after the final dose of this drug will be collected; for ADRs and AEs of VOD/SOS in patients who did not undergo HSCT within 52 weeks after the start of this drug, those that occurred within 52 weeks after the start of this drug will be collected; for ADRs and AEs of VOD/SOS in patients who underwent HSCT within 52 weeks after the start of this drug, those that occurred within 52 weeks after the last HSCT will be collected. The listings will include all events reported in this survey.

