- Myeloblast count before conditioning for the first HSCT after the start of this drug
- Time from the date of final dose of this drug to the date of the first HSCT after the start of this drug
- Treatment cycles [1 cycle, 2 cycles, 3 cycles, 4 cycles, 5 cycles, 6 cycles,  $> 6$  cycles]
- Treatment cycles [ $\leq 3$  cycles,  $\geq 4$  cycles]
- Best overall response
- MRD
- Best overall response and MRD
- Adverse drug reactions that occurred during the treatment period - liver disorder as a safety specification

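### The liver-disorder factor in the early-death-after-HSCT analysis is not cut off at HSCT, so drug-related liver events after transplant can be counted as predictors

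*SAP*

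**What the plan says.** Protocol 7.2 names "risk factors for early death of HSCT patients after BESPONSA treatment" among the research objectives. SAP 8.2.3.3 addresses it with subgroup proportions, risk ratios, plots and tests, and repeats the analysis for non-relapse death. SAP 6.1 defines early death as death within 100 days after the first HSCT following the start of the drug.

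One factor in the list is "Adverse drug reactions that occurred during the treatment period - liver disorder as a safety specification". SAP 5.4 codes it only as "liver disorder as a safety specification [absent, present", with no timing relative to HSCT.

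SAP 2.1 gives the treatment period as "From the start of treatment to Day 28 post-final dose". Protocol 8.7 agrees: "From treatment initiation to Day 28 post-treatment: Safety (e.g., AEs) and efficacy (hematologic remission and survival". Neither ends the period at HSCT. For reactions other than VOD/SOS, SAP 8.2.3 uses the same limit: "those that occurred from the start of this drug to 28 days after the final dose of this drug will be collected". For VOD/SOS in transplanted patients collection runs much longer: "those that occurred within 52 weeks after the last HSCT will be collected". The liver-disorder specification includes VOD/SOS (Protocol 7.1.1).

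SAP 5.4 also plans a factor for the interval from final dose "to the date of the first HSCT after the start of this drug [< 4 weeks, ≥ 4 weeks to < 8 weeks", and so on, so HSCT within 28 days of the final dose is allowed for.

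**The concern.** A risk factor for death after transplant should be known by the time the outcome clock starts. Here the clock starts at the first HSCT, but the factor can still change from absent to present after it. A drug-related VOD/SOS that begins after HSCT and ends in early death would put the patient in the factor-present group, and the death would then count as evidence that the factor predicts death.

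The label also changes meaning with the transplant interval. For a patient transplanted 28 days or more after the final dose, with no later dosing, it describes pre-transplant events only. For a patient transplanted sooner, it mixes pre-transplant and post-transplant events.

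At stake is the interpretation of one factor serving a stated objective. A reader would naturally take it as pre-transplant liver toxicity, and its risk ratio could be inflated by post-transplant complications.

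**Working it through.** **The plan's own figure.** The documents give no numerical figure for this analysis. The only design figure is the 80.4% power for the VOD/SOS comparison. With 88 patients per group and two-sided alpha 0.1, it reproduces: 80.2% at the rounded rates of 18.5% and 6.2%, and 80.4% at 18.45% and 6.15%. It has no bearing on this point.

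**Step 1: the windows.** Count days from the final dose and let HSCT fall on day d.

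- Factor window: start of drug to day 28.
- Outcome window: day d to day d + 100.
- Overlap, if d < 28: the first 28 − d days after HSCT.

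| d | Days after HSCT inside the factor window |
|---|---|
| 7 | 21 |
| 14 | 14 |
| 21 | 7 |
| 28 or more, no later dosing | 0 |

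**Step 2: is it corrected elsewhere?** Other variables are handled differently:

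- Best response and MRD, also in the 8.2.3.3 list, are taken before HSCT or subsequent therapy, whichever is earlier (Protocol 8.8.11.1 and 8.8.11.2).
- ECOG PS and the laboratory factors are anchored before the start of the drug or before conditioning.
- The VOD/SOS summaries in SAP 8.2.3.1 separate events before HSCT from those after it.

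No such rule, landmark or time-dependent handling is given for the liver-disorder factor.

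**Step 3: possible size.** Every input here is an assumption; the documents give none of them.

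- D, early death: 15%, 25%, 35%
- a, pre-HSCT liver reaction, independent of death (true risk ratio 1.0): 10%, 20%
- s, share transplanted while the treatment period is still open: 0%, 10%, 25%, 50%
- q₁ and q₀, in-window post-HSCT liver reaction in early deaths and in others, among that share: 20% and 5%, or 40% and 10%

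Probability of being coded present:

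- early deaths: e₁ = a + (1 − a)·s·q₁
- others: e₀ = a + (1 − a)·s·q₀

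Apparent risk ratio = [D·e₁ / (D·e₁ + (1 − D)·e₀)] ÷ [D·(1 − e₁) / (D·(1 − e₁) + (1 − D)·(1 − e₀))]

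Example with D = 0.25, a = 0.10, s = 0.25, q₁ = 0.40, q₀ = 0.10:

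- e₁ = 0.10 + 0.90 × 0.25 × 0.40 = 0.190
- e₀ = 0.10 + 0.90 × 0.25 × 0.10 = 0.1225
- Risk if present = 0.0475 / (0.0475 + 0.0919) = 0.341
- Risk if absent = 0.2025 / (0.2025 + 0.6581) = 0.235
- Ratio = 1.45

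Over the whole grid:

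| s | Apparent risk ratio (true value 1.0) |
|---|---|
| 0% | 1.00 |
| 10% | 1.05 to 1.23 |
| 25% | 1.12 to 1.53 |
| 50% | 1.22 to 1.96 |

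Counting only pre-HSCT onsets returns 1.00 in every row, by construction.

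**The case against.** The best case for leaving the plan alone has several parts.

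- **Few patients may be affected.** The under-4-weeks category is the lowest bin of an exhaustive scale. It shows that the case is allowed for, not that it is common; the share could be close to zero. This stands, and it is why the size is unknown.
- **The mechanism is narrow.** Only events the physician attributes to the drug count, and the overlap lasts 28 − d days. A reader might infer from the long VOD/SOS follow-up that every VOD/SOS up to 52 weeks after HSCT enters the factor. The treatment-period wording excludes those after Day 28. This stands too; it narrows the problem without removing it.
- **The bias need not be upward.** A patient who dies soon after HSCT has less time to develop an in-window reaction, which pulls the other way. The illustration assumes more in-window reactions among early deaths and does not separately model that shorter time. This is fair.
- **The analysis is exploratory.** SAP 4.1 treats p-values as descriptive, and this is one factor in a long list. So the issue is interpretation, not error control. It still serves a stated objective.
- **VOD/SOS cases can be checked.** The SAP 9 listings give onset relative to transplant. That helps a careful reader but does not change the tabulated risk ratio.

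A reader might also infer that the treatment-cycle factors and the final-dose-to-HSCT interval share the defect, because SAP 9 lists resumption of the drug. The documents do not support this. Resumption is not placed after HSCT, and the histogram of final dose to first HSCT in SAP 8.2.2 starts at 0 weeks, which implies dosing that ended before transplant.

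**Conclusion.** The point holds in a limited form. As defined, the factor can include drug-related liver events that begin after HSCT, in patients transplanted within 28 days of the final dose. Its risk ratio for early death therefore cannot be read cleanly as a pre-transplant association.

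The overlap of windows follows directly from the SAP definitions. The size does not: 1.05 to 1.96 against a true 1.0 rests wholly on assumed inputs, and there is no distortion if no patient is transplanted in that interval.

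Stronger readings are not supported. The assumed range does not establish that the plan will produce a strong spurious risk ratio. The analysis is not uninformative, since the factor is sound for patients transplanted later without further dosing. The liver event is not itself part of the outcome, which is death. The correction is still worth making, because it is small and removes an avoidable ambiguity from a stated objective.

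**What to change.** In SAP 5.4 and 8.2.3.3, define the factor as a liver-disorder adverse drug reaction with onset during the treatment period **and** before the date of the first HSCT after the start of the drug. Report separately the number of patients whose in-window liver reaction began on or after that date, and do not use those events as a predictor.

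Both limits are needed. Liver reactions other than VOD/SOS are recorded only to Day 28 after the final dose (Protocol 8.8.14; SAP 8.2.3), while VOD/SOS is followed much longer. Requiring only onset before HSCT would add late VOD/SOS in patients with long intervals without the matching other liver events. Under the two-limit rule the factor means an on-treatment, pre-transplant liver reaction, and the table should say so; events between Day 29 and a late HSCT remain outside it.

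The cost is a wording change and one extra date comparison. Dosing dates, HSCT dates and event onset dates are already collected (Protocol 8.8.3, 8.8.5 and 8.8.14). Slightly fewer patients will be coded as having the factor, so its risk ratio will be a little less precise. If tables already exist, add the restricted version beside them with the count of post-HSCT onsets.

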#### 8.2.3.4. Subgroup analyses

Patients who experienced at least one AR will be summarized in terms of n and proportion by each of the following factors selected from those specified in Section 5.4. To investigate the correlation between patient characteristics and occurrence of ADRs, statistical tests specified in Section 8.1.3 and risk ratio estimation will be performed.

- Age [ $< 15$  years,  $\geq 15$  to  $< 65$  years,  $\geq 65$  years]
- Age [ $< 18$  years,  $\geq 18$  to  $< 55$  years,  $\geq 55$  years]
- Age [ $< 15$  years,  $\geq 15$  years to  $< 40$  years,  $\geq 40$  years]
- Disease name
- Chromosome karyotype
- Chromosome karyotype \* Philadelphia chromosome is considered positive if the chromosome karyotype is t(9;22).
- Hepatic impairment
- Renal impairment
- Medical history (past) - VOD/SOS
- Medical history (past) - GVHD
- Medical history (past) - Hepatitis or hepatic disease
- Medical history (present) - VOD/SOS
- Medical history (present) - GVHD
- Medical history (present) - Hepatitis or hepatic disease

- ECOG PS before the start of this drug
- AST and ALT levels immediately before the start of this drug
- $\gamma$ -GTP level immediately before the start of this drug
- Total bilirubin level immediately before the start of this drug
- Hemoglobin level immediately before the start of this drug
- Platelet count immediately before the start of this drug
- Peripheral blast count immediately before the start of this drug
- Myeloblast count immediately before the start of this drug
- Salvage line of the induction treatment with this drug
- HSCT before the start of this drug
- Pregnancy \* Pregnancy during the treatment period. Limited to cases in which information on pregnancy is collected

Furthermore, patients who experienced ADRs will be summarized in terms of n and proportion for each SOC and PT by each of the following factors selected from those specified in Section 5.4. In addition, risk ratios for the proportion of patients with ADRs for different subgroups will be determined as per Section 8.1.3 and presented graphically. If, however, there is a category with less than 10 patients and after reconsideration it is considered difficult to determine the risk ratio for the category, it will not be determined for the relevant category. To investigate the correlation between patient characteristics and occurrence of ADRs, statistical tests specified in Section 8.1.3 will be performed.

- Age [< 15 years,  $\geq 15$  to  $< 65$  years,  $\geq 65$  years]
- Age [< 18 years,  $\geq 18$  to  $< 55$  years,  $\geq 55$  years]
- Age [< 15 years,  $\geq 15$  to  $< 40$  years,  $\geq 40$  years]
- Hepatic impairment
- Renal impairment
- HSCT before the start of this drug
- Total dose per cycle  $> 1.8$  mg/m^2
- Pregnancy \* Pregnancy during the treatment period. Limited to cases in which information on pregnancy is collected

Similarly, ADRs meeting definition of liver disorder including safety specification events of VOD/SOS will be analyzed by each of the following factors. Similar analyses will also be performed for ADRs of Grade 3 or higher based on CTCAE v4.0.

- Age [< 15 years,  $\geq 15$  to  $< 65$  years,  $\geq 65$  years]
- Age [< 18 years,  $\geq 18$  to  $< 55$  years,  $\geq 55$  years]
- Age [< 15 years,  $\geq 15$  to  $< 40$  years,  $\geq 40$  years]
- Hepatic impairment
- Medical history (past) - VOD/SOS
- Medical history (past) - Hepatitis or hepatic disease
- Medical history (present) - VOD/SOS
- Medical history (present) - Hepatitis or hepatic disease
- ECOG PS before the start of this drug

- AST and ALT levels immediately before the start of this drug
- $\gamma$ -GTP level immediately before the start of this drug
- Total bilirubin level immediately before the start of this drug
- Platelet count immediately before the start of this drug
- Peripheral blast count immediately before the start of this drug
- Salvage line of the induction treatment with this drug
- HSCT before the start of this drug

Similarly, ADRs meeting definition of safety specification events of myelosuppression will be analyzed by each of the following factors. Similar analyses will also be performed for ADRs of Grade 3 or higher based on CTCAE v4.0.

- Age [ $< 15$  years,  $\geq 15$  to  $< 65$  years,  $\geq 65$  years]
- Age [ $< 18$  years,  $\geq 18$  to  $< 55$  years,  $\geq 55$  years]
- Age [ $< 15$  years,  $\geq 15$  to  $< 40$  years,  $\geq 40$  years]
- Hepatic impairment
- Renal impairment
- Total dose per cycle  $> 1.8 \text{ mg/m}^2$
- ECOG PS before the start of this drug
- White blood cell count immediately before the start of this drug
- Neutrophil count immediately before the start of this drug
- Platelet count immediately before the start of this drug
- Salvage line of the induction treatment with this drug
- HSCT before the start of this drug

Similarly, ADRs meeting definition of safety specification events of infection will be analyzed by each of the following factors. Similar analyses will also be performed for ADRs of Grade 3 or higher based on CTCAE v4.0.

- Age [ $< 15$  years,  $\geq 15$  to  $< 65$  years,  $\geq 65$  years]
- Age [ $< 18$  years,  $\geq 18$  to  $< 55$  years,  $\geq 55$  years]
- Age [ $< 15$  years,  $\geq 15$  to  $< 40$  years,  $\geq 40$  years]
- Hepatic impairment
- Renal impairment
- Total dose per cycle  $> 1.8 \text{ mg/m}^2$
- ECOG PS before the start of this drug
- Salvage line of the induction treatment with this drug
- HSCT before the start of this drug

Similarly, ADRs meeting definition of safety specification events of hemorrhage will be analyzed by each of the following factors. Similar analyses will also be performed for ADRs of Grade 3 or higher based on CTCAE v4.0.

- Age [ $< 15$  years,  $\geq 15$  to  $< 65$  years,  $\geq 65$  years]
- Age [ $< 18$  years,  $\geq 18$  to  $< 55$  years,  $\geq 55$  years]

- Age [ $< 15$  years,  $\geq 15$  to  $< 40$  years,  $\geq 40$  years]
- Hepatic impairment
- Renal impairment
- Total dose per cycle  $> 1.8 \text{ mg/m}^2$
- ECOG PS before the start of this drug
- Salvage line of the induction treatment with this drug
- HSCT before the start of this drug

Similarly, patients who experienced GVHD will be analyzed by each of the following factors. GVHD events included in the analysis will be events of which PT includes GVHD according to the version of MedDRA used for the analysis.

- Medical history (past) - GVHD
- Medical history (present) - GVHD

Similar analyses will be performed for serious ADRs.

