8.8.14. Adverse Events

Pertinent to safety assessment, the status of AEs during the period from the start of BESPONSA treatment to the end date of the observation period in the treatment phase (Day 28 post-treatment) will be confirmed, and the following information will be entered. For VOD/SOS, events during a period from the start of BESPONSA treatment to the end date of the observation period in the follow-up phase will be entered. When an AE is observed, the investigator should take an appropriate therapeutic action and promptly notify it to the sponsor. When the AE is related to BESPONSA, its course should be followed up until the AE or its sequelae resolve or become stable to the extent that is acceptable for the investigator and sponsor.

Also, further investigation should be separately conducted, if deemed necessary by sponsor for patients who experienced a serious adverse reaction, an unexpected adverse reaction or other adverse reactions not listed in the package insert.

- (1) Presence/absence of AE
- (2) Name of AE
- (3) Date of occurrence
- (4) CTCAE v4.0 Grade (worst grade)
- (5) Intervention
- (6) Seriousness
- (7) Outcome at the present
- (8) Causal relationship

Note: An AE is any and all unfavorable event (including clinically significant abnormal laboratory change) occurring in a patient after starting BESPONSA treatment regardless of causal relationship. A serious adverse event (SAE) is any unfavorable medical occurrence that results in death, is life-threatening, requires (or prolongs) hospitalization, causes persistent or significant disability/incapacity, results in congenital anomalies or birth defects, or is other conditions which represent significant health

PFIZER CONFIDENTIAL

Inotuzumab

B1931024 NON-INTERVENTIONAL STUDY PROTOCOL

Amended 8, 12 December 2023

hazards.

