### 5. ANALYSIS SETS

#### 5.1. Safety Analysis Set

The safety analysis set (SAS) is defined as the full analysis set (FAS) that is as close as possible to all patients treated with this drug. Specifically, the SAS consists of all registered or reported patients except those who meet any of the following conditions:

- a. The case report form could not be collected at all. (Indicated as "CRF not collected" in the survey report.)
- b. There was a violation or flaw in the study contract. (Indicated as "Contract violation/flaw" in the survey report.)
- c. There was a violation in the registration. (Indicated as "Invalid registration" in the survey report.)
- d. Administration of the survey drug was not reported at all. (Indicated as "No dosing information" in the survey report.)
- e. The case report form at the original hospital before patient transfer has not been fixed. (Indicated as "No dosing information - dosing information unconfirmed") \* This condition applies only to cases where information of the original hospital and that of the transferred hospital are linked. If the original hospital refuses continued survey or information from the original hospital becomes uncollectible, this exclusion condition is considered not met (the patient will not be excluded because of this exclusion criterion).
- f. Information on adverse events was not reported at all - no visits after the first prescription. (Indicated as "No information on adverse events - no visits" in the survey report.)
- g. Information on adverse events was not reported at all - there is a visit(s) after the first prescription but no record of information. (Indicated as "No information on adverse events - no record" in the survey report.)

For details of each criterion other than e, see the Guidance for Adoption/Rejection Criteria for Analysis Populations and Handling of Data in Special Investigation.

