- White blood cell count immediately before the start of this drug [ $\leq 4000/\text{mm}^3$ ,  $\geq 4000/\text{mm}^3$ , not performed]
- Neutrophil count immediately before the start of this drug [ $\leq 2000/\text{mm}^3$ ,  $\geq 2000/\text{mm}^3$ , not performed]
- Platelet count immediately before the start of this drug [ $< 10 \times 10^4/\mu\text{L}$ ,  $\geq 10 \times 10^4/\mu\text{L}$ , not performed]
- Peripheral blast count immediately before the start of this drug [ $\leq 1000/\mu\text{L}$ ,  $> 1000/\mu\text{L}$ , not performed]
- Myeloblast count immediately before the start of this drug [ $\leq 50\%$ ,  $> 50\%$ , not performed]
- Salvage line of the induction treatment with this drug [Initial induction, 1st, 2nd, 3rd or later]
- HSCT before the start of this drug [not performed, performed]

Subgroup analyses of safety will be performed also for the following factors:

- HSCT after the start of this drug [not performed, performed]
- Type of the first HSCT after the start of this drug [autologous transplant, allogeneic hematopoietic stem cell transplant with myeloablative conditioning, allogeneic hematopoietic stem cell transplant with nonmyeloablative conditioning, unknown]
- Donor of the first HSCT after the start of this drug [alternative donor, matched related donor]
- Conditioning with alkylating agent for the first HSCT after the start of this drug [ $\leq 1$  agent (including no conditioning),  $\geq 2$  agents]
- Conditioning with busulfan for the first HSCT after the start of this drug [not performed (including no conditioning), performed]
- ECOG PS before conditioning for the first HSCT after the start of this drug [0, 1,  $\geq 2$ , not performed]
- AST and ALT levels before conditioning for the first HSCT after the start of this drug [ $\leq 1.5 \times$  the institutional upper limit of normal range (IULN), either  $> 1.5 \times$  IULN, not performed]
- $\gamma$ -GTP level before conditioning for the first HSCT after the start of this drug [ $\leq 50$  IU/L,  $> 50$  IU/L, not performed]

- Total bilirubin level before conditioning for the first HSCT after the start of this drug [≤ institutional upper limit of normal range (IULN), > IULN, not performed]
- Hemoglobin level before conditioning for the first HSCT after the start of this drug [< 10 g/dL, ≥ 10 g/dL, not performed]
- Platelet count before conditioning for the first HSCT after the start of this drug [< 10 × 10^4/µL, ≥ 10 × 10^4/µL, not performed]

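### Myelosuppression ADRs are compared by baseline blood-count class with no at-risk restriction and no worsening-from-baseline rule, so those risk ratios can be distorted in either direction

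*SAP*

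**What the plan says.** SAP 8.2.3.4 sets out the comparison: "Similarly, ADRs meeting definition of safety specification events of myelosuppression will be analyzed by each of the following factors". It adds: "Similar analyses will also be performed for ADRs of Grade 3 or higher based on CTCAE v4.0". The opening word of the first sentence refers back to the analysis by SOC and PT just before it, which gives risk ratios, graphs and tests under SAP 8.1.3. The ratios are unadjusted.

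Three of the listed factors are "White blood cell count immediately before the start of this drug", "Neutrophil count immediately before the start of this drug" and "Platelet count immediately before the start of this drug". In SAP 5.4 their low classes are up to 4000/mm³, up to 2000/mm³ and below 10 × 10⁴/µL. None has a lower limit.

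On the population, SAP 5.1 says: "The safety analysis set (SAS) is defined as the full analysis set (FAS) that is as close as possible to all patients treated with this" […]. None of its exclusions a to g concerns baseline counts or grade.

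Protocol 8.8.14 counts as an AE any unfavorable event "occurring in a patient after starting BESPONSA treatment regardless of causal relationship", and the CRF takes the worst CTCAE grade. SAP 6.1 makes an AE an ADR when the physician attributes it to the drug. SAP 8.2.3.1 keeps the highest grade when an ADR recurs. Neither document requires the grade to have worsened from baseline.

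The analysis serves a stated objective in Protocol 7.2: "Background characteristics possibly affecting the onset of liver disorder including VOD/SOS, myelosuppression, infections and hemorrhage", together with Grade 3 or higher events.

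**The concern.** A risk ratio for the onset of a Grade 3 or higher event is readable when everyone in the denominator can still have that onset. Here the exposure is the baseline value of the count whose later value grades the event. A patient who starts with, say, Grade 3 neutropenia cannot newly reach Grade 3 in that lineage. Whether that patient becomes a case depends on whether the count worsens further and on whether the site records a persisting or deepening cytopenia as an ADR.

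For the matching count, such patients fall in the low class, provided the CTCAE Grade 3 boundary lies inside it. The low-versus-high ratio then reflects reporting practice as well as susceptibility to the drug.

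The reader could not separate the two from the planned tables. SAP 8.2.2 does not tabulate baseline white cells or neutrophils, and it splits platelets only at 10 × 10⁴/µL. Individual laboratory values appear only as a listing in SAP 9. What is at stake is whether a low baseline count is named as a risk factor, or cleared as one, for the wrong reason.

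**Working it through.** **The plan's own figure.** The documents give no figure for this analysis. The only sizing figure is the 80.4% power in Protocol 8.10.2, which is for VOD/SOS. It reproduces: 88 per group at two-sided 0.10 gives 80.2% with the printed rates (18.5% and 6.2%) and 80.4% with 18.45% and 6.15%. It says nothing about myelosuppression.

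**Inputs for one lineage.** None of these is in the documents, so all are assumptions:
- CTCAE Grade 3 or higher counts lie within the low class (the documents print no cut-offs).
- f, the share of the low class already at Grade 3 or higher: 20% to 60%.
- r, the risk of a new Grade 3 or higher ADR in patients still at risk: 30% to 50%, equal in both classes. The true ratio is therefore set at 1.0.
- c, the share of patients already at Grade 3 or higher who are recorded with a Grade 3 or higher ADR of that lineage: 0, 50% or 80%.

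**Formula.** Low-class proportion = f·c + (1 − f)·r. High-class proportion = r. Ratio, low over high, = [f·c + (1 − f)·r] / r = 1 + f·(c/r − 1).

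Example with f = 0.4, r = 0.3, c = 0.8: (0.32 + 0.18) / 0.3 = 1.67. With c = 0: 0.18 / 0.3 = 0.60.

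| r | f | c = 0 | c = 0.5 | c = 0.8 |
|---|---|---|---|---|
| 0.3 | 0.2 | 0.80 | 1.13 | 1.33 |
| 0.3 | 0.4 | 0.60 | 1.27 | 1.67 |
| 0.3 | 0.6 | 0.40 | 1.40 | 2.00 |
| 0.5 | 0.2 | 0.80 | 1.00 | 1.12 |
| 0.5 | 0.4 | 0.60 | 1.00 | 1.24 |
| 0.5 | 0.6 | 0.40 | 1.00 | 1.36 |

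**Reading.** The ratio is below 1 when c < r, above 1 when c > r, and exactly 1.0 only when c = r. With wider ranges (r from 20% to 60%, c from 0 to 100%) the extremes are 0.40 and 3.40; the latter is (0.6 × 1.0 + 0.4 × 0.2) / 0.2.

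**After restriction.** Among patients below Grade 3 for that lineage at baseline, the ratio is r / r = 1.00 for every f and c.

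The reference class is marked by underlining that the available text does not show. If the low class is the reference, the ratios above become their reciprocals.

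**The case against.** The strongest reply is that the outcome is an ADR, not a low count. It must arise after the first dose, and the physician must attribute it to the drug (SAP 6.1). An abnormal test becomes an AE only through one of the triggers in Protocol 10.4.1. This stands, and it defeats one inference a reader might draw: that patients who start with severe cytopenia count as cases regardless of the drug. It leaves the share c undetermined, however, because no trigger compares with baseline and one is simply investigator or sponsor judgement.

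Second, myelosuppression is a grouped outcome, and SAP 6.1 leaves its event list to be specified separately. A reader might infer that every patient with pre-existing severe cytopenia sits in the low class. That holds only for the matching count. A patient with severe thrombocytopenia or neutropenia may have white cells above 4000/mm³, since circulating blasts count as white cells. A patient at Grade 3 in one lineage can also newly reach it in another. The arithmetic therefore describes single-lineage comparisons, which the SOC-and-PT structure plausibly includes, and not the pooled ratio.

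Third, low marrow reserve may genuinely raise risk, and dropping severely cytopenic patients would narrow the question. Both points are fair. The true ratio of 1.0 is a device for isolating the distortion, and the all-patient table should stay.

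Fourth, SAP 4.1 makes testing exploratory, without a significance level. Protocol 8.14 warns about confounding, and SAP 8.2.3.5 allows further analyses. This limits the consequence, but the label does not remove a bias in an estimate. SAP 4.1 also allows a post-hoc threshold for screening, and an optional later analysis is not a plan.

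**Conclusion.** The point holds in a bounded form. For single-lineage Grade 3 or higher ADRs compared by the matching baseline count, the planned ratio can move away from 1 with no difference in new risk, and the documents fix neither its direction nor its size. Under the stated assumptions it is 0.4 to 0.8 with no reporting of pre-existing cases, 1.0 to 1.4 with 50% reported and 1.1 to 2.0 with 80% reported.

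Two further inferences are not supported. One is that patients already at Grade 3 or higher dominate the low class: no baseline distribution is given. The other is that ratios by salvage line, prior HSCT or ECOG PS are distorted in the same way: those factors are not the measurement that grades the outcome, and nothing in the documents shows such an effect.

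The analysis is exploratory, and neither the sample size nor any decision rule depends on it. It does answer a named objective, and the final analysis supports the re-examination application (SAP 3). The change should therefore be made.

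**What to change.** Keep the all-patient table in SAP 8.2.3.4. Derive a baseline CTCAE grade for each lineage from the white cell count, differential and platelet count already collected (Protocol 8.8.8), and add:

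- (a) For Grade 3 or higher ADRs of one lineage, the risk ratio and test by that lineage's baseline class, restricted to patients below Grade 3 for that lineage at baseline. Show patients already at Grade 3 or higher as n/N in a separate row, without a ratio. Patients with no baseline count cannot be graded and should also have their own row.
- (b) For pooled myelosuppression, results split by presence or absence of Grade 3 or higher cytopenia in any lineage at baseline.

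State that the conclusion on baseline counts as risk factors rests on these at-risk results, with the all-patient table as description.

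The cost is SAP text, one derived variable per lineage and extra tables; no new data are needed. The downside is smaller denominators and wider intervals in the added analyses. With f between 20% and 60%, the low class in (a) keeps 80% to 40% of its patients.
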